Assessments: All assessments will be performed at the Anschutz Health and Wellness Center. Participants will also complete the Godin Physical Activity Questionnaire during Visit 1 only. The following assessments will be completed at visits 1, 2, and 3.

A total body DXA scan will be performed to determine body composition. The scan takes approximately 3 minutes, but 15 minutes is allocated for data entry and positioning the patient.

HRV assessments will be performed prior to functional testing, to avoid the potential impact of physical activity on heart rate measures. This assessment will be performed in a private examination room and will take approximately 30 min.

Physical fitness and function assessments will then be performed. These assessments will be performed in the same order at every assessment, with the most fatiguing assessments performed at the end of the session. The order will be: SLS, TUG, grip strength, 30StS, SCT, gait speed, 400MWT. All tests will be performed by the same investigator at all time points.

This investigator is a licensed physical therapist with experience performing functional tests in medically involved or functionally limited populations. A secondary tester, blinded to participant group, will be present at all sessions to provide any necessary assistance and insure lack of testing bias. Participants will also be given the activity tracker to assess ADSC, with instructions on how to use the device and how to return the device in one week. The functional assessment period will take approximately 1 hour.

Questionnaire data will be collected using REDCap software. Participants will have two options for completing questionnaire data at each assessment: 1) completion of questionnaire data via emailed REDCap survey at the Health and Wellness Center via provided computer or tablet, 2) completion of printed questionnaires provided at the functional assessment. Data obtained from participants completing printed questionnaires will be entered in the REDCap system by two study investigators independently to insure accuracy, following which hardcopies will be destroyed.

If participants will not receive a standard blood draw as part of their medical care within a one-week window of the visit, they will be transported to the CTRC where the necessary blood draw will be performed.

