Exercise Adaptations: Prior to the start of exercise sessions, participants will be questioned on significant changes in symptoms or the presence of new symptoms (such as nausea or fever), which will be used to modify the exercise session (intensity and components) for that day to allow maximum symptom-limited participation. Participants will be encouraged to complete three sessions per week for at least eight weeks during neoadjuvant therapy. Exercise intensity, components, and time will be recorded for each exercise session to guide the exercise specialist in making appropriate exercise adjustments (progression, maintenance, or reduction). Exercise programs have been found to be safe in cancer survivors, even during life-threatening treatments², but safety has not been investigated specifically in the current population. Common risks may include muscular fatigue and soreness, as well as transient increases in treatment-related symptoms. Rarer risks include the possibility of injury due to unknown bone metastases or acute cardiac events. Intensity and acute changes in symptoms will be closely monitored to decrease these risks.

Participants will schedule their sessions with the exercise specialists administering the program, typically taking place between 8AM and 4PM, Monday through Friday, at the

Anschutz Center for Health and Wellness. Adherence will be measured as the percent of scheduled sessions attended. Exercise sessions will also be individualized to participants on a day to day basis, with time and intensity not exceeding that listed above. Prior to the start of exercise sessions, participants will be questioned on significant changes in symptoms or presence of new symptoms (such as nausea or fever), which will be used to modify the exercise session for that day. Exercise intensity, type, and time will be recorded for each exercise session.

Standard Care: Participants in the Standard Care group will receive no exercise intervention, but will continue to receive standard follow-ups, treatments and services from their oncology team. The services that participants receive as standard care include their medical care, symptom control, social worker support, and nutrition.

Participants in all groups will receive \$50 reimbursement for each Visit completed, totalling \$150.00 for all three Visits.

D. Description, Risks and Justification of Procedures and Data Collection Tools:

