Risks of exercise and assessments: Certain risks are associated with performing exercise in any population, as well as specifically in cancer survivors. The likely risks of exercise include muscular fatigue and/or soreness, acute increase in fatigue, joint stiffness or soreness, and possible acute increase in treatment- or cancer-related symptoms. The more serious risks include fracture associated with unknown bone metastases, development of ventricular arrhythmia, myocardial infarction, cardiac arrest, and death.

Justifications and Protection: For adults in the general population and for cancer survivors in particular the benefits of exercise training outweigh the risks. Exercise interventions have been shown to be safe in multiple cancer survivor populations¹². The discomforts of exercise training and testing will be explained to the participants. Participants will be informed that they can choose to withdraw or not participate in some or all portions of the study at any time for any reason. Before, during, and at the conclusion of each exercise training and testing session, study personnel will ask participants about new or worsening signs and symptoms. Every exercise session will be supervised by qualified study personnel who are versed in exercise training for clinical populations and BLS-certified. Exercise intensity and types of exercise will be adapted for each individual participant to match their capacity throughout the study. Exercise tests and training will be of submaximal intensity. Exercise intensity will be monitored by study personnel to decrease likelihood of an acute cardiac event, and participants will be monitored for symptoms including chest pain, acute shortness of breath at rest, or dizziness. Patients will be instructed to stay well-hydrated, and will be monitored for symptoms of dehydration including headache, confusion, tachycardia, significantly increased respiratory rate, and changes in skin elasticity. Patients with diabetes will be monitored for symptoms of hypoglycemia, encouraged to bring snacks to assessments and exercise sessions, and snacks and juice will also be stocked by research personnel.

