These risks will be minimized by not including personal identifying information on the forms, when possible, and by conducting interviews and collection of personal information in a private setting. Direct data entry into a secure website using REDCap software will be coded with a unique participant number.

Data Safety and Monitoring: Research personnel will monitor safety concerns on an ongoing basis as data is collected and analyzed. The study PI will review the safety of the protocol at least monthly and submit an annual report. A medical safety officer ([name]), who is not an investigator on the study, will review the safety of the study after enrollment of every 10 participants and submit a report at least annually. Study participants will be informed that they can choose to stop the study (exercise intervention or assessments) at any time. If study personnel deem that the participant is no longer physically capable of performing the exercise intervention or assessments, the participant will be discontinued from the study. The overall protocol will be discontinued if the PI, research team, and safety officer agree that participants in the exercise group are experiencing significant negative outcomes, not experienced in the non-exercise (control) group, attributed to the exercise intervention or testing.

The PI will report all unanticipated problems and adverse events to COMIRB within 5 days of occurrence. Unanticipated problems and adverse events are defined as by COMIRB.

E. Potential Scientific Problems:

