Potential Problems and Solutions: Given that no previous studies of preoperative exercise programs exist in patients with pancreatic cancer, the power analysis for the current study was based on the outcomes of a study of preoperative exercise in patients with lung cancer. It is possible that the estimated sample size here will not provide enough power to detect differences in postoperative outcomes. Regardless of statistical significance, outcomes from this study will provide the basis to allow future studies in this population that are adequately powered. Study groups will not be randomized, resulting in a potential selection bias and baseline differences. The decision to design the study as a non-randomized trial was made to improve recruitment for the target patient population and the short duration of the funding period. Analysis of the number of participants who are willing and able to participate in an exercise intervention at the AHW will determine if a randomized trial is feasible and allow a better estimate of a realistic enrollment period. We will interpret our enrollment activity as

follows: if less than 70% of anticipated enrollment is achieved, we will conclude that additional study sites will be needed to enroll sufficient numbers of patients treated with neoadjuvant therapy for pancreatic cancer for formal hypothesis testing in a RCT.

The individualized nature of the exercise program precludes rigorous control of exercise components between participants. An individualized exercise program may increase adherence and will allow adaptability to acute changes in the patients' health status due to treatment- or disease-related symptoms. The neoadjuvant therapy period will vary between participants, resulting in a variable duration of the exercise intervention. The duration of exercise must remain variable to avoid deconditioning that would be caused by a long lapse between the end of the exercise intervention and surgery. Most patients complete 16 weeks of neoadjuvant therapy before surgery, which will result in a typical exercise intervention lasting 12 weeks. We will record the duration of exercise training and neoadjuvant therapy and test these factors as covariates in the analyses of the fitness, function, and stress outcomes.

F. Data Analysis Plan:

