The timeline for this protocol is estimated at 2 years. Data collection (participant recruitment and intervention) is estimated at 1 - 1.5, after which data will be analyzed and manuscripts prepared.

Data Analysis and Anticipated Outcomes: Groups will be compared on demographic variables such as age and gender. Variables that differ significantly will be included in planned analyses as covariates. Statistical significance will be defined as $\alpha \leq 0.05$, however, results will be interpreted cautiously as is warranted for pilot studies⁴⁴. As we expect to be underpowered to test for statistical interactions, multiple tests will be used to assess differences in baseline measures, change scores, and postoperative outcomes between groups. Change scores will be calculated as the difference between Visit 2 and Visit 1. Groups will be compared using non-parametric exact k-sample permutation tests, which are well suited for small sample sizes as they do not rely on typical normal-theory methods⁴⁵.

Aim 1: The feasibility of implementing this intervention will be assessed by quantifying the accrual rate of patients willing and able to participate in the preoperative exercise intervention and individual patients' adherence to the prescribed exercise program (percentage of scheduled sessions attended). Safety will be determined by the number of non-serious and serious adverse events and relatedness of the events to exercise, as described by COMIRB.

Aim 2: Hypothesis 1 – Baseline physical fitness and function measures and change scores will be compared between groups using exact k-sample permutation tests. We anticipate a significant difference in the changes from Visit 1 to Visit 2, with the Exercise group demonstrating maintained or improved physical fitness and function compared to the Control group, with no differences in baseline measures. A secondary analysis will be used to describe the trajectory of changes in physical function from visits 1, 2, and 3.

Hypothesis 2 – Postoperative outcomes will be compared with exact k-sample permutation tests (hospital length of stay) or Fisher's exact tests (hospital readmission) between the Exercise and Control groups. We anticipate the Exercise group to have a significantly lower hospital length of stay and occurrence of hospital readmission compared to the Control group.

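### Symptoms are asked about far more often in exercisers than in controls, so any use of controls as a safety reference would tend to overstate non-serious events with exercise

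*Combined protocol and SAP*

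**What the plan says.** Section IV.D (Justifications and Protection) sets the rule on asking: "at the conclusion of each exercise training and testing session, study personnel will ask participants about new or worsening signs and symptoms". The same sentence also requires asking before and during each session. Section IV.C (Exercise Adaptations) adds, for exercisers: "Prior to the start of exercise sessions, participants will be questioned on significant changes in symptoms or the presence of new symptoms".

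On the number of sessions, section IV.C says "Participants will be encouraged to complete three sessions per week for at least eight weeks during neoadjuvant therapy". Section IV.E describes the usual length of neoadjuvant therapy, "which will result in a typical exercise intervention lasting 12 weeks". Testing is common to both groups: "The following assessments will be completed at visits 1, 2, and 3" (section IV.C, Assessments). Under Standard Care, controls have no training sessions and see their oncology team as usual. The record review 30 days after discharge retrieves length of stay and unplanned readmission. No schedule or method for collecting adverse events from controls between visits is given.

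The information is used in two places. Section IV.F, Aim 1, says "Safety will be determined by the number of non-serious and serious adverse events and relatedness of the events to exercise". Section IV.D (Data Safety and Monitoring) provides for discontinuing the protocol if the principal investigator, research team and safety officer agree that exercisers are "experiencing significant negative outcomes, not experienced in the non-exercise (control) group, attributed to the exercise intervention or testing". The safety officer reviews safety after every 10 enrolments.

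**The concern.** Both groups receive neoadjuvant therapy, so fatigue, nausea and similar complaints will occur in both. The exercise risks listed in section IV.D include transient rises in treatment- and cancer-related symptoms, which a single case does not distinguish from background. The control group is the natural internal reference for that background, yet it is the group asked least often.

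A symptom that controls are never asked about can pass as one that they did not have. That matters for the discontinuation statement, for any table of Aim 1 events by group, and for relatedness judgements that lean on what controls report. The expected direction is too many non-serious events in the exercise group relative to controls.

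**Working it through.** The plan states no figure for safety ascertainment, so there is none to reproduce. The number of asking occasions can be derived from its text.

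**Inputs.** Three sessions a week; 8 weeks minimum (section IV.C) and 12 weeks typical (section IV.E); three testing visits in both groups (section IV.C). Attendance is an outcome of the study, so 100% and an assumed 50% are shown. That controls are asked only at the three visits is an inference: these are the only sessions described for them.

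**Asking occasions per participant** = 3 × weeks × attendance + 3, against 3 in controls.

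| Weeks | Attendance | Exercise | Control | Ratio |
|---|---|---|---|---|
| 8 | 100% | 24 + 3 = 27 | 3 | 9 |
| 12 | 100% | 36 + 3 = 39 | 3 | 13 |
| 8 | 50% (assumed) | 12 + 3 = 15 | 3 | 5 |
| 12 | 50% (assumed) | 18 + 3 = 21 | 3 | 7 |

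Counting three prompts per session multiplies both sides by three and leaves the ratio unchanged.

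**From asking to recorded events.** This step needs figures that the protocol does not give. Two illustrations show the range, both with no true effect of exercise and full attendance.

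*Equal yield per query (upper end).* If each query independently has chance p of recording an event, the share of participants with at least one is 1 − (1 − p)^k. For 12 weeks, k is 39 against 3:

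- p = 0.02: 1 − 0.98^39 = 55%, against 1 − 0.98^3 = 6%
- p = 0.05: 86% against 14%
- p = 0.10: 98% against 27%

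This gives a query covering two or three days the same yield as one covering about 12 weeks. In effect, controls report nothing from earlier in the interval.

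*Limited recall.* Suppose that a brief symptom is reported only if someone asks within L days. Take the interval from Visit 1 to Visit 2 as equal to the training period (84 or 56 days), with sessions on Monday, Wednesday and Friday. The longest gap between sessions is then 3 days, so with L of 3 or more every episode in an exerciser is caught. In controls the share caught is L divided by the length of the interval.

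| L (days) | 12 weeks: controls | Ratio | 8 weeks: controls | Ratio |
|---|---|---|---|---|
| 7 | 7/84 = 8% | 12 | 7/56 = 12.5% | 8 |
| 14 | 14/84 = 17% | 6 | 14/56 = 25% | 4 |
| 30 | 30/84 = 36% | 2.8 | 30/56 = 54% | 1.9 |

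With complete recall the ratio is 1 and the artefact disappears; shorter recall makes it larger. The direction is clear, but the size depends on recall, which is unknown.

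**The case against.** The strongest reply is that the plan contains no between-group safety analysis to bias. Aim 1 concerns the feasibility of the exercise programme, and section IV.F names no group contrast for adverse events, although it names tests for Aim 2 and the exploratory aim. This stands. A reader might infer that the Aim 1 safety conclusion is invalid, or that equal true rates will appear as harm. The documents do not support either: the first use of controls is in the discontinuation statement, and that also requires significant outcomes, attribution to exercise or testing, and agreement of three parties. Those conditions soften the bias. They do not remove it, because absence in controls remains one of the conditions, and attribution itself is hard without a sound background rate. An error here would be towards caution, which limits the risk to participants but not the distortion of what is reported.

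It can also be said that session questions are there to adapt the session, that the items listed for recording at each session are intensity, components or type, and time, and that adverse events follow an institutional definition not reproduced in the protocol. How many answers become adverse events is therefore unknown. This also stands, and is a further reason not to attach a size to the bias. It does not supply a collection route for controls.

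FACIT-Fatigue and FACT-G are collected alike in both groups at the three visits, and the general safety monitoring is not confined to exercisers. These give some symmetric information, but they are not adverse-event collection between visits. Lastly, serious events such as fracture or infarction would probably surface in routine care whatever the questioning.

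**Conclusion.** The concern holds in a limited form. As written, the plan asks exercisers about symptoms on roughly 5 to 13 times as many occasions as controls. The lower end rests on assumed 50% attendance, and the whole range on the inference that controls are asked only at visits. Any comparison that uses controls would tend to overstate non-serious events with exercise; serious events are much less exposed.

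A 13-fold difference in asking should not be read as a 13-fold difference in recorded events. The percentages from the equal-yield calculation are upper-end illustrations, and the bias itself cannot be sized from the documents. Frequent questioning of exercisers is sound protection and is not the fault. What is missing is a matched collection in controls, or a rule that confines group comparisons to events gathered in the same way.

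**What to change.** Leave session questioning as it is, for participant protection. Then:

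- Collect adverse events for any group comparison with the same short form, the same recall period and the same fixed intervals in both groups. REDCap is already in use, but section IV.C describes its survey as completed on site. Controls may have transport or distance barriers, so allow remote, telephone or paper completion.
- Apply the same health-record review for adverse events in both groups from Visit 1 to surgery.
- State in section IV.F that between-group safety statements, including by-group tables shown to the safety officer, rest only on these two sources.
- Report session-elicited events for the exercise group alone, as events per session attended, and label them so.

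The wording of the discontinuation statement stays with the sponsor and the safety officer.

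For 30 participants the cost is minor participant burden and a short record review. The intervention and sample size do not change. Control events that were never asked about may not be recoverable later, so the change is worth making early. It will not cure the self-selection of a non-randomized comparison, which section IV.E already acknowledges, and exercisers used to frequent questioning may still report somewhat more on a common form.

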The potential participant population will be individuals who receive a diagnosis of borderline-resectable pancreatic cancer (adenocarcinoma), being treated at the University Hospital Cancer Center. These inclusion and exclusion criteria will apply to participants in both groups.

Inclusion Criteria: Recent (< 4 week) first diagnosis of a borderline-resectable pancreatic adenocarcinoma, assigned to receive neoadjuvant therapy and surgery at University of Colorado Cancer Center, physician clearance to participate in exercise program, and age 21-80 years.

Exclusion Criteria: Any significant comorbid conditions that would interfere with or preclude participation in an exercise intervention, including orthopedic conditions such as advanced osteoarthritis, mobility-limiting amputations or chronic injuries, or mobility-limiting acute orthopedic injuries; advanced rheumatoid arthritis; widespread chronic pain conditions such as fibromyalgia; pulmonary conditions such as chronic obstructive pulmonary disease, emphysema, interstitial lung disease, use of supplemental oxygen; known cardiovascular disease, uncontrolled hypertension, or new cardiac event within the past 6 months. Participants with a second cancer diagnosis at the time of enrollment will be excluded.

Sample size estimation: No studies have previously investigated the effects of preoperative exercise in patients with pancreatic cancer. In patients with lung cancer, a preoperative exercise program reduced hospital length of stay by 4 days compared to usual care⁴⁰. Based on this difference, with a SD of 3, 12 participants would be required in each the experimental and control groups ($\alpha = 0.05$, $\beta = 0.90$ ⁴¹). To account for overall attrition, groups will be increased by 3 participants each, based on a study of preoperative exercise after neoadjuvant treatment in patients with rectal cancer showing an overall attrition of 28%⁴². A total of **30 participants (15 per group)** will be recruited for this study.

C. Study Design and Research Methods

This is a prospective, non-randomized, parallel group, intervention control trial, patterned on a similar pilot study in patients with rectal cancer⁴².

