Recruitment: Participants will be recruited from the University Hospital Cancer Center. Patients with a recent diagnosis (< 4 weeks) of pancreatic cancer will be given information on the study by their treating physicians and asked if they would be interested in participating. If yes, physicians will have patients complete a HIPAA A form to provide study personnel with their name. Study personnel will access the patients' medical records to evaluate the inclusion/exclusion criteria. If these criteria are met, research personnel will meet with the

potential participant at the University of Colorado Cancer Center to provide information about the study. If patients are still interested in participating, the familiarization and possibly first visit will be scheduled. Participants will have the option of combining the familiarization session and Visit 1. All data collected during screening will be destroyed and recollected after obtaining written consent in patients choosing to participate. If the inclusion/exclusion criteria are not met after review of the health record, the patient will be contacted and the exclusion decision will be explained.

Group Assignment: Volunteers meeting the inclusion and exclusion criteria and willing to participate in the exercise intervention will be assigned to the exercise group. The standard of care, non-exercise control group will comprise volunteers who meet the inclusion and exclusion criteria but are unable to commit to participation in the exercise intervention for practical reasons (e.g. barriers in transportation or home location). The use of a non-randomized study design is to maximize patients participating in the exercise program to determine accrual rate, program adherence, and safety while still allowing a non-exercise control group.

Protocol:

[figure not shown]

Figure 1

Figure 1 shows the event timeline of the study, with time points of visits and intervention in relation to diagnosis and surgery. Written informed consent will be obtained by a study investigator during a familiarization period, where participants will have assessments and the exercise investigation explained in-depth. There will be four time points for data collection: pre-intervention (Visit 1), post-intervention and preoperative (Visit 2), 30-day postoperative (data retrieved from electronic health record), and follow-up (Visit 3).

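### The number willing to exercise is only an upper bound on the number who could be randomised, so it cannot settle whether a randomised trial is feasible or how long it would take to enrol

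*Combined protocol and SAP*

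**What the plan says.** Section IV.C describes the design: "This is a prospective, non-randomized, parallel group, intervention control trial". Under Group Assignment, eligible volunteers "willing to participate in the exercise intervention will be assigned to the exercise group", while controls are eligible volunteers who "are unable to commit to participation in the exercise intervention for practical reasons". The reason given there is: "The use of a non-randomized study design is to maximize patients participating in the exercise program to determine accrual rate, program adherence, and safety". Section IV.E adds a second reason: "The decision to design the study as a non-randomized trial was made to improve recruitment for the target patient population".

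Section IV.E then draws the inference at issue. The count of patients "who are willing and able to participate in an exercise intervention at the AHW will determine if a randomized trial is feasible". The same sentence expects it to give a better idea of a realistic enrolment period. One decision rule follows: "if less than 70% of anticipated enrollment is achieved, we will conclude that additional study sites will be needed".

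The analysis plan for Aim 1 (Section IV.F) measures accrual in the same terms, by "quantifying the accrual rate of patients willing and able to participate in the preoperative exercise intervention". Section IV.G says accrual will serve as a reference for the time frame of later studies.

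**The concern.** The count answers one question and is used for another. It records who will take up exercise when exercise is guaranteed. A randomised trial needs patients who will also enter knowing that chance may give them standard care. Nobody in this study faces that choice, and no form, visit or analysis records how they would respond to it.

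This concerns the exercise volunteers themselves. Section IV.E acknowledges selection bias and baseline differences, but that limits the comparison of outcomes between groups. It does not limit the feasibility statement.

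What is at stake is the planning of the next trial. If accrual here is good and is read as showing that randomisation is feasible, that trial could be started with too few sites or too short an enrolment period. No effect estimate, test, adherence result or safety result in the present study is affected.

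**Working it through.** **Inputs from the documents**
- Planned enrolment: 30, 15 per group (Section IV.B, sample size estimation).
- Enrolment rule: 70% of anticipated enrolment (Section IV.E).
- Entry to each group: Section IV.C, Group Assignment.

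**Input not in the documents**
- q, the share of willing exercisers who would also accept randomisation. It is neither given nor collected. I assume 0.5 to 1.0, for illustration only; the upper end means no overstatement.

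**Step 1. Origin of the 15.** The plan uses a 4-day difference, SD 3, alpha 0.05 and power 0.90 (the printed beta of 0.90 is read as power). Two-sided, by the normal approximation:

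n = 2 × (1.960 + 1.282)² × 3² / 4² = 11.8, rounded up to 12 per group.

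This matches the plan. Adding 3 for attrition gives 15 per group and 30 in all. The point below does not depend on this calculation; 15 is used only as the planned number of exercisers.

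**Step 2. Direction.** Let W be the number willing and able to exercise, and R the number of those who would also accept allocation by chance. R is a subset of W, so R = q × W ≤ W, with equality only at q = 1. This holds for the same site, eligibility criteria, period and exercise programme, with standard care as control.

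**Step 3. Size for assumed q.** If W accrues at a given rate, the projected time to reach a target is target / rate. The time under randomisation is target / (q × rate), so the ratio is 1/q. The target of 30 randomised is borrowed from this study; the documents give no size for a future trial.

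| Assumed q | Randomisable among 15 (15 × q) | Enrolment time relative to projection (1/q) | Willing patients needed to randomise 30 (30/q, rounded up) |
|---|---|---|---|
| 1.0 | 15 | 1.00 | 30 |
| 0.8 | 12 | 1.25 | 38 |
| 0.6 | 9 | 1.67 | 50 |
| 0.5 | 7.5 | 2.00 | 60 |

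**Step 4. The 70% rule.** Anticipated enrolment is not defined. If it means the planned 30, the threshold is 0.70 × 30 = 21.
- *Below the threshold:* total enrolment is at least W, and W is at least R. If total enrolment is below 21, R is below 21 too, so the conclusion that more sites are needed holds.
- *At or above the threshold:* nothing follows about R. With 21 enrolled and an even split (assumed), 10.5 are exercisers. R is then 10.5 × 0.5 = 5.25 to 10.5 × 1.0 = 10.5 over the assumed range. The rest are controls who by definition could not commit to exercise.

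**Step 5. What the plan implies about q.** Sections IV.C and IV.E both say randomisation was avoided to raise participation or recruitment. That suggests the investigators expect accrual to be lower under randomisation, but gives no value for q.

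**The case against.** The strongest reply is that the protocol claims less than the quoted sentence suggests. Aim 1 concerns the feasibility of providing the exercise programme, and for that the willing-and-able count is the right measure. Section IV.G rests feasibility of larger-scale implementation mainly on adherence and treats accrual only as a reference for timing. The non-randomised design and its recruitment motive are stated openly, and the study calls itself a pilot whose results call for caution. All of this stands, and it is why the count should be kept. It does not remove the sentence in Section IV.E that makes the count decide whether a randomised trial is feasible.

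Three stronger readings are tempting, and the documents support none of them.
- *That the count is shown to overstate randomisable accrual by a definite factor.* It is shown only to be an upper bound. Full acceptance is not excluded, and any factor depends on an assumed q.
- *That the plan contains a biased go/no-go rule.* The only rule is one-sided: a shortfall leads to more sites, not to abandonment, and no positive conclusion is attached to meeting the threshold. An upper bound is sound evidence for that negative conclusion.
- *That the projected enrolment period is necessarily too short by 1/q.* That also assumes a future trial with the same site, eligibility and standard-care control. Section IV.E itself contemplates additional sites, and no future control condition is specified.

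It can also be said that a hypothetical question only swaps one upper bound for another. That is fair, but the new bound lies at or below the present one, and it addresses the right question.

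**Conclusion.** The concern holds in a limited form. The willing-and-able count is an upper bound on the number who could be randomised at this site, exact only if every willing exerciser would accept randomisation. The direction follows from the assignment rule and needs no numerical assumption. The size cannot be obtained from the documents; on an assumed acceptance of 0.5 to 1.0, 15 exercisers correspond to 7.5 to 15 randomisable patients, and enrolment takes 1 to 2 times as long as projected.

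The weakness lies in two inferences: reading adequate accrual as evidence that a randomised trial is feasible, and taking the enrolment period from it. The change is worth making before enrolment, because the missing information cannot be recovered cleanly once participants have begun to exercise.

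**What to change.** Make two changes.

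1. Reword Section IV.E so that the willing-and-able count is reported as exercise uptake and as an upper bound on randomisable accrual, and no longer as what decides the feasibility of a randomised trial. The 70% rule can stay, with a note that reaching the threshold does not itself show that randomisation is feasible.
2. Add one yes/no item at the consent and familiarisation visit, before exercise starts: would the participant have joined if chance had decided between the exercise programme and standard care? Report the number able to exercise who answer yes as a tighter upper bound. Use that number for the statement on randomised-trial feasibility and enrolment period.

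The cost is one question at an existing visit and a reworded sentence or two; design, group assignment and sample size are unchanged. The drawback is that the answer is hypothetical, carries no consequence for the participant, and probably still overstates true acceptance. It should be labelled accordingly. If the item is not added, the rewording alone would still correct the inference, but the study would then say nothing about acceptance of randomisation.
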